Review Adverse Events ⁴	X	X	X	X	X	X	
SABR		X					
Pembrolizumab			X	X			
Review Prior/Concomitant Medications	X	X	X	X	X		
New Anti-Cancer Therapy Status					X	X	X
Survival status						X	

Trial Phase:	Screening Phase	Treatment Phase			Follow-up Phase		Progression
Trial phase and windows	Screening -28 to -1	SABR Within 4 weeks of randomisation	Day 1 Cycle 1 7 days \pm 2 days from SABR	Day 1 Cycle 2-34 3 days \pm 2 days prior to each dose of pembrolizumab	Safety Follow-up 30 days \pm 3 days from date of last dose of pembrolizumab	Follow-up 3 months \pm 7 days from the last cycle of pembrolizumab	Upon first progression ¹
Laboratory Procedures/Assessments: analysis performed by LOCAL laboratory							
Haematology ⁵	X		X	X			As clinically indicated
Biochemistry ⁶	X		X	X			
Thyroid Function tests ⁷	X		X	X			
Coagulation profile ⁸	X		X	X			
Virology ⁹	X						
Tumour Evaluation							
CT scan (Brain, Chest, Abdo, Pelvis) reported with RECIST 1.1 or MRI ¹⁰	X			X		X	
Whole body bone scan ¹⁰ (if clinically indicated)	X			X		X	
Response assessment ¹⁰				X		X	
FDG-PET ¹⁰	X			X ¹¹			
Translational studies							
Metastatic tumour biopsy sample ¹²	X					X	X
Primary tumour biopsy sample ¹³	X						
Blood Collection ¹⁴ (serum and ctDNA)		X	X	X		X	X

Table 2: ARM 2 Schedule of events

Trial Phase:	Screening Phase	Treatment Phase			Follow-up Phase		Progression
Trial phase and windows	Screening -28 to -1	Day 1 Cycle 1 3 days \pm 2 days prior to the first dose of pembrolizumab	SABR 7 days \pm 2 days from cycle 1 day 1	Day 1 Cycle 2-34 3 days \pm 2 days prior to each dose of pembrolizumab	Safety Follow-up 30 days \pm 3 days from date of last dose of pembrolizumab	Follow-up 3 months \pm 7 days from the last cycle of pembrolizumab	Upon first progression ¹
Clinical/Administrative Assessments							
Informed Consent	X						
Inclusion/Exclusion Criteria	X						
Demographics and Medical History	X						
Disease Specific Medical History including prior therapies	X						
SINS score for Spinal Targets	X						
Full Physical Examination	X	X		X			
Vital Signs and body measurements ²	X	X		X		X	
ECOG Performance Status	X	X		X		X	
Pregnancy Test (β -HCG) ³	X	X		X			
Review Adverse Events ⁴	X	X	X	X	X	X	
SABR			X				
Pembrolizumab		X		X			
Review Prior/Concomitant Medications	X	X	X	X	X		
New Anti-Cancer Therapy Status					X	X	X
Survival status							X
Laboratory Procedures/Assessments: analysis performed by LOCAL laboratory							
Haematology ⁵	X	X		X		As clinically	

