6. Biochemistry: calcium chloride, glucose, phosphorus, potassium, sodium, magnesium, total protein, Liver Function Tests: Albumin, Alkaline Phosphatase (ALP), Alanine Aminotransferase (ALT), Aspartate Aminotransferase (AST), Lactate Dehydrogenase (LDH), Gamma-Glutamyl Transferase (GGT), total bilirubin (+direct bilirubin if total bilirubin is elevated above the ULN), Kidney Function Tests: Urea, creatinine.
7. Thyroid Function tests: T3, T4 and TSH. To be performed at during screening, day 1 cycle and every 6 weeks thereafter.
8. Coagulation Profile: PT (INR), aPTT.
9. Virology: HIV, Hepatitis B and C tests only required for those patients at risk of prior or current active infection as determined by the investigator. To be performed within 21 days of randomisation.

Tumour evaluation

10. Radiological tumour assessments will be performed by CT scan (or MRI as required if tumour is in extremity) at screening (within 6 weeks of randomisation), prior to cycle 3, 5, 7 and every 3 cycles thereafter in the treatment phase. Then 3 monthly in the follow-up phase until the last patient recruited completes 24 months of follow-up, unless evidence of progression earlier. Whole body bone scan (WBBS) will be performed if clinically indicated at the same time points. Formal response assessment (using RECIST 1.1, irRECIST, Peter Mac Metabolic Response Criteria and PERCIST 1.0.) at each scheduled scan time point. Response should be confirmed with repeat imaging 4 to 8 weeks later by the same imaging modality. CT of brain only required at screening.
11. FDG PET at baseline and prior to cycle 5 of pembrolizumab. (note: a contemporaneous CT brain/chest/abdo pelvis performed at the same time will fulfill the CT requirement 3 month follow-up)

Biological Evaluations

12. A fresh biopsy of the primary or metastatic lesion will be performed at screening (within 12 weeks of randomisation). and 3 months post completion of SABR. This will ideally be the same site as biopsied before at screening. In event of disease progression, a sample from progressing metastatic site(s), if feasible, is requested. Refer to the SABRseq laboratory manual for further details on handling and shipping of tumour samples.

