5.3 Endpoints

Primary Endpoint

- Toxicities associated with SABR in combination to pembrolizumab are defined as adverse events (AE's) considered possibly, probably or definitely related to the treatment. Safety (acute and long term) will be assessed using CTCAE version 4.03.

Secondary Endpoints:

- Response will be assessed by 4 different methods (RECIST 1.1, irRECIST, Peter Mac Metabolic Response Criteria and PERCIST 1.0) and will be assessed a) only considering irradiated lesions; b) only considering non-irradiated lesions and; c) considering all lesions (overall response rate)
- Overall survival will be measured from the date of randomisation to the date of death from any cause.
- Progression free survival will be measured from the date of randomisation to the date of first progression at any site or date of death due to any cause.
- Event history is defined as the time from the date of randomisation to the date of each event of interest (progression at an irradiated lesion, progression at a non-irradiated lesion, appearance of a new lesion, ceasing treatment and death). Patients alive will be censored at the date of last follow-up.

Exploratory Endpoints

A number of translational endpoints will be evaluated including:

- PD-L1 expression in tumour tissue using immunohistochemistry with the 22C3 antibody using the DAKO Autolink 48 system.

- Tumour infiltrating lymphocytes (TILs).
- Changes in host anti-tumour immunity to look for evidence of immune activation and relief of immunosuppression in tumour tissue and peripheral blood from the patient over time and at time of progression (if this occurs).
 - Blood samples will be collected at multiple time points before, during and after trial related therapies. These will be analysed for biomarkers including, but not limited to, the following (this is a non-exhaustive list):
 - Absolute lymphocyte counts using a blood analyser.
 - The presence of CD8+ T cells by flow cytometric analysis.
 - Change in frequency of tumour reactive T cells. These may include markers for HLA-DR, CD4+, CD8+ T cells, PD-1, TIM-3 signifying antigen presentation and experience.
 - Immune cytokines

6. Trial Design

This is a prospective, open label, two arm randomised clinical trial with 1:1 allocation ratio evaluating the safety, efficacy and immunological effects of two different sequences of pembrolizumab in combination with SABR treatment in NSCLC – pembrolizumab given either before or after SABR.

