7.2 Exclusion Criteria

The patient must be excluded from participating in the trial if the patient:

1. Has had previous high dose radiotherapy (biological equivalent of >30Gy in 10#) to an area to be treated which includes vertebral bodies (see below).

Note: Previous high dose radiotherapy is defined as a biological equivalent dose to above that of 30 Gy in 10 fractions using an alpha/beta ratio (50) of 3. Where a patient has received radiotherapy to an equivalent or lower dose than defined above, stereotactic radiotherapy of the area may be considered. In doing so, assessment of the volume and total dose received by any overlap region must be made, and documented by generating a cumulative plan incorporating both the previous and current treatment fields. It is the treating radiation oncologist's responsibility to review both the current plan and the cumulative plan inclusive of previous radiotherapy.

2. Has had previous thoracic radiotherapy of > 36Gy within the 6 months prior to randomisation.
3. Has known active central nervous system (CNS) metastases and/or carcinomatous meningitis. Patients with small asymptomatic or previously treated brain metastases may participate provided they are stable (without evidence of progression by imaging for at least four weeks prior to the first dose of trial treatment and any neurologic symptoms have returned to baseline), have no evidence of enlarging brain metastases, and are not using steroids for intracranial neurological symptoms at least 7 days prior to trial randomisation. This exception does not include leptomeningeal disease which is excluded regardless of clinical stability.
4. Has evidence of Spinal Cord Compression.
5. Has a Spinal Instability Neoplastic Score ≥ 7 unless lesion reviewed by a neurosurgical service and considered stable (see Appendix 2).
6. Requires surgical fixation of bone lesion for stability. All surgical fixation and instrumentation must be completed before randomisation on study.
7. Is currently participating and receiving study therapy or has participated in a study of an investigational agent and received study therapy or used an investigational device within 4 weeks of randomisation.
8. Has a diagnosis of immunodeficiency.
9. Has a known history of active TB (Bacillus Tuberculosis)
10. Has a hypersensitivity to pembrolizumab or any of its excipients.

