8.2.3 Cycle 2 to Cycle 34 Assessments

The following assessments will be performed within 3 days prior to pembrolizumab dosing in each cycle, unless otherwise specified.

- Physical examination
- Vital signs and weight
- Documentation of concomitant medications
- Documentation of ECOG performance status
- Laboratory studies including FBE, biochemistry and coagulation, hepatic and kidney
- Thyroid function tests (every 6 weeks)
- Radiological evaluation with a CT Chest/Abdomen and Pelvis or MRI (prior to cycle 3, 5, 7 and every 3 cycles thereafter)
- FDG-PET scan prior to cycle 5
- Whole body bone scan (prior to cycle 3, 5, 7 and every 3 cycles thereafter, only if clinical indicated)
- Response assessment (prior to cycle 3, 5, 7 and every 3 cycles thereafter)
- Adverse events assessment
- Pregnancy test in female patients with child bearing potential.
- Blood samples for correlative studies

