13.1 Evaluation of response by RECIST1.1 and irRECIST

The same imaging modality as used at screening (i.e. CT or MRI scans) should be used at every visit. Changes only in the largest diameter (unidirectional measurement) of the tumour lesions are used in the RECIST v1.1 criteria. For tumour lymph nodes, the short axis must be measured. Lesions are measurable or non-measurable using the definitions described below. Refer to Appendix 3 and 4.

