3.7 Evaluation of overall response

Target lesions	Non-target lesions	New lesions	Overall response
CR	CR	No	CR
CR	Non-CR/non-PD	No	PR
CR	Not evaluated	No	PR
SD	Non-PD or not all evaluated	No	SD
Not all evaluated	Non-PD	No	Not evaluable
PD	Any	Yes or No	PD
Any	PD	Yes or No	PD
Any	Any	Yes	PD

Source: Eisenhauer *et al*, 2009 (see References)

Appendix 4

irResponse Evaluation Criteria in Solid Tumors (irRECIST)

Adapted from irRECIST - ESMO 2014 abstract 4958

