1.5. Baseline: Brain Lesions

- Lesions detected on brain scans can be considered as both target or non-target lesions.

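### After screening no brain imaging is scheduled, so PFS at any site and time to new lesion in effect measure extracranial plus clinically detected CNS progression, while Appendix 4 still allows brain lesions as targets

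*Combined protocol and SAP*

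**What the plan says.** **Who enters.** Exclusion 3 in Section 7.2 makes an exception to the bar on CNS disease: "Patients with small asymptomatic or previously treated brain metastases may participate provided they are stable".

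**How brain lesions count.** Appendix 4 (irRECIST), item 1.5: "Lesions detected on brain scans can be considered as both target or non-target lesions". Appendix 3 (RECIST 1.1) does not mention brain targets. Its item 3.4 asks for targets that represent all involved organs and records every other lesion as non-target.

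**What is scanned.** The imaging row in Tables 1 and 2 reads "CT scan (Brain, Chest, Abdo, Pelvis) reported with RECIST 1.1 or MRI" and is marked at screening, on treatment and in follow-up. It carries footnote 10, which ends: "CT of brain only required at screening". The on-treatment list for Arm 1 (Section 8.2.3) has "Radiological evaluation with a CT Chest/Abdomen and Pelvis or MRI (prior to cycle 3, 5, 7 and every 3 cycles thereafter". Sections 8.3.3 and 8.5 name the same body regions, without the brain.

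**What consistency is required.** Section 13.1: "The same imaging modality as used at screening (i.e. CT or MRI scans) should be used at every visit". Appendix 3 (3.2) goes further and wants each lesion reported at baseline to be followed with the same method and technique.

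**What the endpoints claim.** Section 5.3: "Progression free survival will be measured from the date of randomisation to the date of first progression at any site", or to death. Event history, in the same section, includes the appearance of a new lesion.

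**The concern.** The lesion rules and endpoint definitions assume that the brain is followed. The imaging schedule does not follow it.

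Two things are at stake. First, PFS and time to new lesion carry an any-site definition that the scheduled imaging cannot deliver. Asymptomatic growth of a known brain lesion, or a new one, would be recorded only if symptoms or an unplanned scan revealed it. This concerns every patient, not only those with known brain disease. Second, a brain lesion recorded at baseline and not scanned again affects the response category under Appendix 3 (3.7), and Section 14 does not say how a not-evaluable patient enters the response rate.

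**Working it through.** **Step 1. The plan's own figures.** Table 10 gives 8 of 16 responses as 50% (25–75). The exact (Clopper-Pearson) interval is 24.7–75.3%, so it reproduces. Table 9 gives 0.815 per arm at a 10% toxicity rate: 1 − 0.90^16 = 0.815. Neither table depends on brain imaging, so the sample size rationale is untouched.

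**Step 2. PFS and new lesions, by comparing the passages.**
- Section 5.3 counts progression at any site and the appearance of new lesions.
- Footnote 10 and Sections 8.2.3, 8.3.3 and 8.5 schedule no brain imaging after screening.
- What the schedule can capture is extracranial progression at planned scans, CNS progression found through symptoms or an incidental scan, and death.
- Against the any-site definition, silent CNS events are dated late or not at all, so times tend to be too long. The brain rule is the same in both arms.
- The documents give no CNS progression rate, so the size of this effect cannot be calculated.

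**Step 3. Which brain lesions can be targets.**
- Previously irradiated lesions are not measurable unless progression in them is documented (Appendix 3, 3.1). Lesions with any prior intervention are likewise not targets without demonstrated progression (Appendix 4, 1.7).
- Non-nodal lesions under 10 mm are non-measurable (Appendix 3, 3.2; Appendix 4, 1.1).
- This leaves untreated, stable lesions of at least 10 mm, or treated ones with documented progression, that the reader actually selects.

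**Step 4. Effect on the response category (Appendix 3, 3.7).**
- Brain target not scanned, no progression elsewhere: the target set is incomplete and the overall response is not evaluable.
- Brain non-target not scanned, targets in CR: overall PR. The planned rate in Section 14.7 is CR+PR, so it does not change.
- Targets stable, non-targets "not all evaluated": overall SD, unchanged.
- The table as read has no row for targets in PR. I assume overall PR, in line with the rows around it. Appendix 4 (2.2) says directly that non-target lesions do not affect irPR.

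**Step 5. Size per not-evaluable patient.** Section 14.3 counts any treated patient with a CT or PET at the visit as response-evaluable, Section 14.4 imputes nothing, and neither says how a not-evaluable result is counted. Starting from 8/16 = 50.0%:

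| Handling of one not-evaluable patient | Rate | Change (points) |
|---|---|---|
| Responder counted as non-responder | 7/16 = 43.8% | −6.25 |
| Responder dropped | 7/15 = 46.7% | −3.3 |
| Non-responder dropped | 8/15 = 53.3% | +3.3 |
| Non-responder counted as non-responder | 8/16 = 50.0% | 0 |

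The two results for dropped patients depend on the starting count; 8/16 is an illustration.

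**Step 6. How many patients.** The documents give no prevalence of brain metastases at entry. Assuming 5% to 20:% of 32 gives 0.05 × 32 = 1.6 to 0.20 × 32 = 6.4 patients with any brain metastasis. By Step 3, those with a selected brain target are a subset of these, possibly empty.

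**The case against.** The strongest reply is that footnote 10 sets a minimum. It does not forbid further brain scans, and a site that records a brain lesion has reason to re-scan it under Section 13.1 and Appendix 3 (3.2). Footnote 11 also contemplates a CT that includes the brain alongside the PET before cycle 5. This stands in part: a reader might infer that the brain is never re-imaged, and the documents do not say that. But footnote 11 is a permission at one time point, and the same-technique rule applies only to lesions already recorded. Neither schedules a search for new brain lesions.

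A second reply is that the table row is not a true contradiction, because footnote 10 qualifies it. That is fair, and it settles what is required. It does not align the endpoint and target-lesion rules with that requirement.

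A third reply concerns response. A reader might infer that patients with brain metastases generally become not evaluable or lose responses. Steps 3 and 4 do not support that. Appendix 3 (3.4) also wants targets suited to repeated measurement, which argues against choosing a lesion with no planned re-scan. In addition, the explicit permission for brain targets is in the irRECIST appendix, while the not-evaluable row is in the RECIST 1.1 appendix; irRECIST keeps its own not-evaluable category for exceptional cases.

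Two further inferences also fail. The brain rule does not favour either sequence, since both arms share it. The 3-month mean survival with brain metastases in Section 4.1 cannot be carried over to this trial, which requires stable CNS disease, ECOG 0–1 and life expectancy above 3 months.

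**Conclusion.** The point holds in a limited form. On the schedule as written, PFS at any site and time to new lesion are in effect extracranial progression plus symptomatic or incidentally imaged CNS progression. They tend to be too long in both arms, with no evident differential bias. This needs no assumption about how many patients enter with brain metastases, but its size cannot be derived from the documents.

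The response effect is secondary and narrow. It requires a brain lesion selected as a target and then not re-scanned. The number of such patients is unknown and may be zero. From 8/16, each shifts an arm's rate by about 3 to 6 points wherever the counting rule moves it, in a direction that the plan does not fix. An unscanned non-target brain lesion removes CR but leaves CR+PR as it was.

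The affected endpoints are all secondary. The primary safety endpoint and the sample size are not affected.

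**What to change.** Reconcile footnote 10, the imaging rows in Tables 1 and 2, Sections 8.2.3, 8.3.3 and 8.5, and Appendix 4 (1.5).

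With the imaging schedule unchanged:
- State that brain lesions may not be target or response-determining lesions.
- Report overall response as extracranial.
- Label PFS and new-lesion time in Sections 5.3 and 14.6 as extracranial progression, clinically detected CNS progression or death, as each applies.

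This costs wording only. The downside is a narrower stated endpoint.

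If the sponsor instead re-images known brain metastases at the scheduled visits, a head series is added to existing visits for that subset and their baseline lesions can be assessed. The PFS and new-lesion label is still needed, because new brain lesions in the other patients would remain unscreened. If brain lesions stay eligible as targets, Section 14.7 should also say how a not-evaluable result is counted.

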4.1 Metastatic Non-Small Cell Carcinoma

Non-small cell carcinoma (NSCLC) is the ninth most common cancer in Australia and the fourteenth most common cancer worldwide (1, 2). The incidence of NSCLC is rising, particularly in patients aged 70 to 90 years (3). Overall, 17% of patients present with metastatic disease and another 50% of patients initially treated with curative intent will develop metastatic disease (4, 5). Historically patients with metastatic non-small cell carcinoma (mNSCLC) have a poor prognosis, with 5-year survival rates of ≤10% (6). In patients with metastatic disease, the median survival time ranges from 6 to 12 months, and in patients with brain metastases, the mean survival time is 3 months (7, 8).

4.2 Stereotactic Ablative Body Radiotherapy and Evidence in Oligometastatic Malignancies.

There is a large body of literature on SABR for oligometastatic malignancies. For practical reasons only the landmark SABR oligometastatic studies will be summarized to highlight tolerability and efficacy.

Salama and colleagues (1) reported on patients with 1 to 5 metastatic cancer sites based on 18F-fluorodeoxyglucose positron emission tomography (FDG-PET) imaging and a life expectancy of at least 3 months who were treated with SABR. Patients received escalating doses of RT, starting at a dose 24Gy (three 8Gy fractions) 2Gy per fraction dose-escalations and a dose ceiling of 60Gy (three 20Gy fractions). The commonest metastatic sites treated were lung (36.3%), lymph nodes (19.4%), liver (19.4%), bone (13.3%) and adrenal glands (8.0%). At a median follow up of 20.9 months no dose limiting toxicity was seen. One patient with a centrally located right upper lobe metastases who received 36Gy (three 12Gy) fractions developed haemoptysis 10 months after SABR. CT and bronchoscopy revealed disease recurrence and this patient died shortly afterwards. More recent studies due to toxicity recommend excluding central lung lesions outside the contexts of clinical trials (2).

A number of phase I and II studies of SABR to spinal metastasis have demonstrated favourable local disease control rates (86-90%) for patients without spinal cord compression (3-6). Similar to intracranial stereotactic radiosurgery, SABR has been shown to be effective in the retreatment of metastases that progress following standard EBRT (7). Additionally, SABR has been shown to be very effective in palliating pain associated with spinal metastases (8, 9).

Several Phase I and II studies have investigated SABR for hepatic metastases using fixed RT doses (10), escalation RT doses (11, 12) and normal tissue complication probabilities (13). These studies have consistently demonstrated high rates of disease control in the treated metastatic deposits (71-92%). However in general liver metastases control rates have been lower than observed in pulmonary or spinal metastases which may reflect challenges in defining the true extent of the metastatic target as well as organ motion with respiration.

Several studies examining SABR for oligometastases in the lung with both single dose (14) and dose-escalation (15) have demonstrated high rates of treated-metastasis control (89-96%) with promising 2-year survival rates (38-39%).

